#### Clinical Event Committees:

Independent, blinded, external committees will be managed by BI's third party preferred provider and set up for adjudication of pancreatic, cerebrovascular, and cardiovascular events. Details on the composition of each of the committees, their respective procedures and interaction will be provided in separate Clinical Event Committee (CEC) charters that will be filed in the TMF.

### **3.2 DISCUSSION OF TRIAL DESIGN, INCLUDING THE CHOICE OF CONTROL GROUPS**

Due to its mechanism of action and the low risk for hypoglycaemia induction, DPP-4 inhibitors like linagliptin should provide additional efficacy alongside manageable tolerability and safety in elderly patients when added to background antidiabetic therapy consisting of basal insulin, metformin (optional), and/or alpha-glucosidase inhibitors (optional).

Elderly patients with T2DM who have insufficient glycaemic control will enter the trial and receive either double-blind linagliptin or placebo. The placebo-controlled design is considered ethically acceptable on the basis of the benefit and risk assessment, as defined in [Section 2.3](#); appropriate criteria for patient discontinuation, ability to adjust or change permitted antidiabetic therapy to maintain, or obtain sufficient level of glycaemic control, as defined in [Section 4.2.1](#); and relevant local and regional guidelines for optimized standard of care.

The randomised treatment period is planned for 24 weeks because the primary efficacy endpoint of HbA1c has been shown to reflect glycaemic control over the preceding 12 weeks and this period should allow sufficient time to demonstrate changes in the incidence of hypoglycaemia events. The 1-week Post-Treatment period is considered to be sufficient, as previous trials with linagliptin have shown that the pharmacodynamic effect of linagliptin only extends to about 7 days after the last dose.

The permitted background antidiabetic therapy will not be provided as part of the clinical trial supplies, unless required by local laws and regulations.

The rationale for dose and dose-interval selection is described in [Section 4.1.3](#).

### 3.3 SELECTION OF TRIAL POPULATION

This is an international trial in which approximately **300 patients (100 patients from Japan)** will be randomised to treatment (**150 patients to each treatment group**).

It is expected that at least 4 to 8 patients should be enrolled (or screened) at each trial site. If enrolment is delayed, additional trial sites may be recruited.

The IRT system will permit each trial site to randomise up to 30 patients. The TCM may allow the randomisation of additional patients after a careful assessment of potential bias due to the patient distribution across trial sites. Permission for a trial site to randomise more than 30 patients must be obtained from the TCM in writing, via the Clinical Monitor Local at BI, in order to increase the number of patients allowed to be randomised at the trial site.

Screening of patients for this trial is competitive (i.e., when a sufficient number of patients have been screened and/or randomised to study medication, screening of patients for the trial will end at all trial sites). **It is possible that recruitment for countries may be stopped while recruitment in Japan continues in order to achieve the required 100 patients randomized in Japan.** Investigators will be notified when a sufficient number of patients have been screened and of the date on which screening will finish. The date that screening may end could be within a 24 hour period of time depending on enrolment numbers. Therefore, investigators may need to contact patients in order to cancel planned screening visits. The investigators will not be allowed to recruit additional patients for this trial after the date that screening has ended. Patients who have completed Screen procedures prior to notification of the termination of recruitment will be allowed to continue in the trial if they meet all entry criteria and are able to follow the visit schedule specified in this protocol.

Patient eligibility will be assessed by a complete medical history, which may be obtained by the investigator verbally from the patient during a trial site visit but is required to be documented in a source document by the investigator (including past medical records of **at least 1 year**), physical examination, and laboratory tests as described in this protocol. Judgement of the clinical relevance of a concomitant disease is at the discretion of the investigator. Conditions under therapy are always clinically relevant.

A log of all patients included into the trial (i.e., having given informed consent) will be maintained in the ISF at the trial site irrespective of whether they have been treated with study medication or not.

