#### 7.5 RANDOMISATION

The sponsor will arrange for the randomisation as well as packaging and labelling of study medication. Eligible patients will be randomly assigned to one of the two treatment groups, with equal allocation of treatments. The randomisation list will be generated using a validated system, which involves a pseudo-random number generator so that the resulting treatment sequence will be both reproducible and non-predictable.

The randomisation will be stratified by HbA1c (< 8.5% vs. ≥ 8.5%) as determined from the blood sample taken at Visit 1 and insulin dose (< 40 international units total daily dose vs. ≥ 40 international units total daily dose) as determined at the beginning of the placebo run-in period (Visit 2). To ensure appropriate representation of patients with insulin doses of < 40 international units total daily dose as well as ≥ 40 international units total daily dose, the trial team will monitor the proportion of patients being recruited into these categories. The limitation of recruitment of a particular category may be arranged (on trial level and/or country level).

The allocation process will be performed at Visit 3 through IRT. However, the IRT allocation and randomization will not increase the study medication bottles at each trial site based on stratification.

Access to the code will be restricted to dedicated randomisation personnel and any exceptional access to the code (in case of an emergency) will be documented according to the sponsor's SOPs.

The trial will only be unblinded after all eCRF and electronic data have been entered into the trial database, after queries have been resolved, and after the database has been locked. Access to the codes will be controlled and documented by a signed confidentiality statement, which will be stored in the TMF.

Practical aspects of the treatment allocation process and methods to carry out blinding are detailed in [Sections 4.1.2](#) and [4.1.5](#), respectively.

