**A total of 300 patients will be randomised.**

Proprietary confidential information.

© 2015 Boehringer Ingelheim International GmbH or one or more of its affiliated companies. All rights reserved.

This document may not - in full or in part - be passed on, reproduced, published or otherwise used without prior written permission.

Based on pooled data from the 1218.36 and 1218.63 trials [REDACTED] assuming a standard deviation of 1.2% in both groups in the FAS with a 0.77% difference in HbA1c change from baseline in treatments, a number of 150 patients in each treatment arm will show superiority with a power >99%. This determination of power is based on a Student's t-test and a two-sided significance level of 5%.

Software package nQuery version 7.0 was used to derive the sample size.

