6.5 POOLING OF CENTRES

This section is not applicable as no analysis by centre will be performed.

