7.5.2 Secondary endpoints

Proportion of patients with at least one hypoglycaemia accompanied by a glucose value during 24 weeks of treatment

Logistic regression for the proportion of patients experiencing at least one hypoglycaemia after 24 weeks will be performed on the FAS (OC); all on-treatment hypoglycaemias will be considered:

- up to drug stop date if a patient prematurely discontinues (Japanese patients that prematurely discontinue prior or at day 175)

- up to trial medication stop date – 1 if a non-Japanese patient does not prematurely discontinue
- up to day 175 if a Japanese patient does not prematurely discontinue prior day 176.

The model will include *treatment* as fixed effect and *baseline HbA_{1c}* and *baseline daily basal insulin dose* as linear covariates.

Frequencies regarding the number and percentage of patients experiencing at least one hypoglycaemia accompanied by a glucose value during 24 weeks in each treatment group will also be presented based on FAS(OC) .

Proportion of patients with HbA_{1c} on treatment <8.0% after 24 weeks of treatment

Logistic regression for the patients achieving HbA_{1c} <8.0% at Week 24 will be performed on FAS (NCF); patients who do not complete 24 weeks of treatment will be considered non-responders. The model will include *treatment* as fixed effect and *baseline HbA_{1c}* and *baseline daily basal insulin dose* as linear covariates. Patients with baseline HbA_{1c} <8.0% will be excluded from the analysis.

A frequency table with the number and percentage of patients with HbA_{1c} <8.0% at Week 24 in each treatment group will be also be presented based on FAS (NCF).

Proportion of patients with HbA_{1c} on treatment <7.0% after 24 weeks of treatment

Logistic regression for the patients achieving HbA_{1c} <7.0% at Week 24 will be performed on FAS (NCF); patients who do not complete 24 weeks of treatment will be considered non-responders. The model will include *treatment* as fixed effect and *baseline HbA_{1c}* and *baseline daily basal insulin dose* as linear covariates. Patients with baseline HbA_{1c} <7.0% will be excluded from the analysis.

Frequencies regarding the number and percentage of patients with HbA_{1c} <7.0% at Week 24 in each treatment group will be also be presented based on FAS (NCF).

Proportion of patients with HbA_{1c} lowering by at least 0.5% after 24 weeks of treatment

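### Japan is a fixed third of the sample, yet no visible primary or secondary model adjusts for region; adding the term would be a small, cheap gain in precision

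*Protocol*

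**What the plan says.** Protocol 3.1 and 3.3 set a total of about 300 randomised patients, 100 of them Japanese. Section 3.3 allows other countries to close while Japan stays open "in order to achieve the required 100 patients randomized in Japan".

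Protocol 7.5 states the stratification rule, which opens "The randomisation will be stratified by HbA" (the quote breaks at the subscript). There are two factors: Visit 1 HbA1c below 8.5% or not, and total daily insulin dose at Visit 2 below 40 units or not. Country appears only as a level at which recruitment of an insulin-dose category may be limited.

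The models that can be read in the SAP are:

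- HbA1c MMRM (7.4.1): treatment, week, treatment by week, baseline HbA1c, baseline basal insulin dose, baseline HbA1c by week.
- Hypoglycaemia and the three HbA1c responder endpoints (7.5.2): logistic models with treatment, baseline HbA1c and baseline basal insulin dose.
- FPG MMRM (7.5.2): the same approach, with baseline FPG and its interaction with week.

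None has a region, country or Japan term. SAP 6.5 adds that "no analysis by centre will be performed", but that concerns centres, not region.

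For hypoglycaemia, SAP 7.5.2 counts events in Japanese completers "up to day 175 if a Japanese patient does not prematurely discontinue prior day 176". For other completers it counts to the day before the medication stop date.

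**The concern.** Region is known before randomisation, recorded for everyone, and by design splits the sample one third to two thirds. The SAP also handles the two regions differently: Japanese patients continue to Week 52, have their own Week 24 visit window, and have their own cut-offs for safety data and hypoglycaemia. If HbA1c change or hypoglycaemia rates differ by region, a model without region leaves that variation in the error, and a chance imbalance in Japanese patients between arms carries into the treatment contrast. At stake is some precision, mainly for hypoglycaemia, and protection against argument after unblinding if the Japanese third happens to fall unevenly.

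**Working it through.** **Inputs.** From the documents: 300 patients, 150 per arm, 100 from Japan, SD 1.2%, difference 0.77%, two-sided 5%, Visit 98 planned on day 169, last dose the day before. Assumed, because the documents give no figures: regional differences in HbA1c change and in hypoglycaemia rate, and an odds ratio of 0.55 for hypoglycaemia.

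**1. The plan's own power.** The protocol calculates "assuming a standard deviation of 1.2% in both groups in the FAS with a 0.77% difference". Standard error = 1.2 × √(2/150) = 0.1386. 0.77/0.1386 = 5.557, and Φ(5.557 − 1.960) = 99.98%. The noncentral t with 298 degrees of freedom also gives 99.98%. The stated power above 99% is reproduced.

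**2. Chance imbalance.** If nothing constrains allocation within Japan, the number of Japanese patients in one arm is hypergeometric (300, 100, 150). The mean is 50 and the SD is √[150 × (1/3) × (2/3) × (150/299)] = 4.09, with a 95% range of 42 to 58. A split of 55:45 or worse has probability of about 27%, and 60:40 or worse about 2%.

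**3. Shift in the HbA1c contrast.** Shift = regional difference × difference in Japanese share between arms.

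- At 55:45 the share differs by 10/150 = 0.067. Regional differences of 0.2% to 0.4% shift the contrast by 0.013% to 0.027%.
- At 58:42 the share differs by 16/150 = 0.107. Regional differences of 0.3% and 0.5% shift it by 0.03% and 0.05%.

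**4. HbA1c precision.** For a regional difference d, a region term removes variance d² × (1/3) × (2/3). With d = 0.2% the residual SD is √(1.44 − 0.0089) = 1.196; with d = 0.8% it is √(1.44 − 0.1422) = 1.139. Power is 99.98% to 99.99%, so nothing changes.

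**5. Hypoglycaemia shift from a rate gap.** At 55:45, regional gaps of 15 to 20 points shift the arm difference by 0.067 × 15 = 1.0 to 0.067 × 20 = 1.3 points.

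**6. Hypoglycaemia shift from the window alone.** Taking the stop date as the last-dose day, 168, the non-Japanese window ends on day 167 and the Japanese window on day 175. That is 8 days, or 8/167 = 4.8% longer (1 to 15 days across the ±7-day visit window). At constant hazard, p becomes 1 − (1 − p)^(175/167): 20% becomes 20.9% and 50% becomes 51.6%. Even at 58:42 this moves the arm difference by only 0.09 to 0.17 points.

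**7. Hypoglycaemia power.** The first four rows use 20,000 simulated trials each, comparing a test without region to a Mantel-Haenszel test stratified by region, as a stand-in for the logistic models. The last row is a logistic simulation with 2,500 runs.

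| Assumed placebo rate, Japan / other | Gap (points) | Power without region | Power with region |
|---|---|---|---|
| 40% / 40% | 0 | 67.7% | 67.6% |
| 50% / 30% | 20 | 63.2% | 64.5% |
| 60% / 30% | 30 | 60.9% | 64.9% |
| 70% / 30% | 40 | 56.6% | 63.3% |
| 20% / 45% | 25 | 61.1% | 62.6% |

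With an odds ratio of 1, the test without region rejects in 4.9% to 5.3% of trials across the first four scenarios.

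**8. The two window rules.** SAP 6.7 treats measurements up to 7 days after medication stop as on-treatment and says this applies to hypoglycaemia as an efficacy endpoint. SAP 7.5.2 stops at the stop date (premature discontinuation), the stop date minus 1 (non-Japanese completers) or day 175 (Japanese completers). For a non-Japanese completer with last dose on day 168, the first rule ends on day 168 + 7 = 175 and the second on day 167. Both cannot be applied.

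**The case against.** The other side has a good deal right.

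- **Redactions.** Parts of the SAP between 7.4.1 and 7.7 are blacked out, and one sentence on the primary model breaks off in a redaction. A regional sensitivity or subgroup analysis could sit there. A reader might infer that the trial never looks at region; the documents do not support that, and the point is limited to the models that can be read.
- **The window.** A reader might infer that counting Japanese patients for longer biases the hypoglycaemia comparison. It does not: within each region both arms share the same cut-off, and step 6 puts the chance effect below 0.2 points. Day 175 looks like an administrative cut for patients who stay on treatment to Week 52. The window is therefore no reason by itself for a region term.
- **Assumed regional differences.** No document states that HbA1c change or hypoglycaemia differs by region. The 1.5-point gain at a 25-point gap has a Monte Carlo error of √(0.611 × 0.389/2,500), about 1 point per figure. The planned covariates may already absorb part of any regional difference.
- **Allocation.** The documents do not say that Japan is unbalanced, only that balance there is not enforced by a stratum. Block structure is not stated, and blocking could make late Japan-only recruitment more even than step 2 suggests.
- **Necessity.** Both stratification factors are already covered by continuous covariates. Leaving out an unstratified factor keeps the randomised test valid, and the trial is powered on HbA1c alone.

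All of this stands as a limit on size. None of it is a reason to leave out a recorded factor that covers a fixed third of the sample.

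**Conclusion.** The point holds as a minor improvement. Region is neither a stratum nor a term in any readable primary or secondary model. The consequence is unadjusted chance imbalance, not bias or lost validity. For HbA1c the effect is negligible: a 55:45 split moves the contrast by 0.013% to 0.027% against a planned 0.77%, under assumed regional differences of 0.2% to 0.4%. For hypoglycaemia the power change is about 0 to +1.5 points for gaps of 0 to 25 points, and about 4 to 7 points only if the gap is 30 to 40 points. These figures rest on an assumed odds ratio of 0.55, assumed regional rates, and allocation that is unconstrained within Japan. The conflict between SAP 6.7 and 7.5.2 needs none of these assumptions; it is there in the text.

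**What to change.** In SAP 7.4.1 and 7.5.2, add region (Japan or other) as a fixed categorical effect to the HbA1c and FPG MMRMs and to the hypoglycaemia and responder logistic models, and fix this before unblinding. The cost is SAP wording and one parameter per model; with no regional gap the simulated power loss is 0.1 points. The logistic odds ratio would then also be conditional on region, as it already is on HbA1c and insulin dose, and the text should say so. The randomisation does not need to change.

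As a separate edit, state one hypoglycaemia on-treatment rule and make SAP 6.7 and 7.5.2 agree on it for premature discontinuations, non-Japanese completers and Japanese completers.

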#### 3.3.1 Main diagnosis for study entry

The trial will be conducted in elderly patients with T2DM on stable basal insulin, metformin (optional), and/or alpha-glucosidase inhibitors (optional) with insufficient glycaemic control, who may or may not be on a diet and exercise program per standard local clinical practice, prior to entry.

Proprietary confidential information.

© 2015 Boehringer Ingelheim International GmbH or one or more of its affiliated companies. All rights reserved.

This document may not - in full or in part - be passed on, reproduced, published or otherwise used without prior written permission.

### 3.3.2 Inclusion criteria

1. Patients must sign and date an Informed Consent consistent with International Conference on Harmonisation (ICH) / Good Clinical Practice (GCP) guidelines and local regulations prior to any evaluation and participation in the trial.
2. Male and female patients with a clinical diagnosis of T2DM, at the time of Informed Consent, who are:
  - a. **60** years of age or older at informed consent or Screen Visit,
  - b. taking stable doses of basal **or biosimilar basal** insulin [strictly inclusive of: insulin neutral protamine Hagedorn (NPH), **Humalog Basal® (a suspension of insulin lispro protamine)**, and isophane insulin; insulin degludec; insulin detemir; and insulin glargine] for at least 4 weeks prior to randomisation (Visit 3) with dose adjustments up to a maximum of +/- 20% of baseline being allowed,
  - c. may or may not be taking metformin immediate release or extended release [if the patient is taking metformin, stable dose must be maintained for at least 12 weeks without dose adjustments prior to randomisation (Visit 3)], and
  - d. may or may not be taking alpha-glucosidase inhibitors [acarbose, miglitol, and voglibose; if the patient is taking alpha-glucosidase inhibitors, stable dose must be maintained for at least 12 weeks without dose adjustments prior to randomisation (Visit 3)].
3. Patients must have an HbA1c of **7.0%** [**53** millimoles per mole (mmol/mol)] to 10.0% (86 mmol/mol) at the first visit (Screen).
4. Patients must have a BMI of 45 kg/m^2 or less at the Screen Visit.
5. In the investigator's opinion, patients must be reliable, compliant, and agree to cooperate with all planned future trial evaluations as explained in detail during the informed consent process and to be able to perform them.

### 3.3.3 Exclusion criteria

Patients with, who are, who have, or who have had:

1. Impaired cognitive ability as supported by the Saint Louis University Mental Status Examination ([R14-0995](#), [R14-0977](#), [R14-0992](#)), additional assessment if necessary (as described below), and verified by the investigator at Screen. Saint Louis University Mental Status Examination scores of **21 to 26** for those patients with high school education or **20 to 24** for those patients who did not complete a high school education indicate that the patient probably **has mild neurocognitive disorder and may be further evaluated as noted below**.

Proprietary confidential information.

The investigator may complete an additional assessment based on typical activities of daily living so that **mild neurocognitive disorder** can be ruled out if the investigator believes that a patient does not have **mild neurocognitive disorder** as supported by the score on the Saint Louis University Mental Status Examination. Patients with **dementia scores on this assessment of 1 to 20 with a high school education equivalent or 1 to 19 without a high school education equivalent must not proceed with further evaluations in the Screen Visit.**

Note: High school or upper secondary education (completing approximately 12 grade levels) equivalents may include the following examinations or certificates such as General Certificate of Education, Leaving Certificate, Reifezeugnis or Abitur, Apolyterion, Baccalaureate, Matura, Swiadectwo Dojrzalosci, Maturity, Studentereksamen, Ylioppilastutkintodistus or Studentbetyg, Diploma de Maturitate, Corso de Orientacion Universitaria, Senior High School Grad, Gymnasium, Higher Preparatory Examination, Higher Commercial Examination, Higher Technical Examination, Bachillerato, University Entrance Certificate, Senior Certificate, National Senior Certificate, Joint Matriculation Board Certificate, Advanced Level Exams, National Senior Certificate or Matric examination.

2. Depressed mood as supported by a score of 10 or more on the Patient Health Questionnaire ([R13-3779](#)) at the Screen Visit.
3. Type 1 Diabetes Mellitus as determined by past medical records and history.
4. Acute coronary syndrome [non-ST Elevation Myocardial Infarction (STEMI), **STEMI, and/or unstable angina pectoris**], stroke or transient ischemic attack within 3 months prior to Screen Visit.
5. Indication of liver disease determined during Screen and/or Run-In Period, defined by a serum level above 3 times the upper limit of normal (ULN) in any of the following: alanine aminotransferase [ALT or called serum glutamic pyruvic transaminase (SGPT)], aspartate aminotransferase [AST or serum glutamic oxaloacetic transaminase (SGOT)], or alkaline phosphatase. Gilbert-Meulengracht syndrome (also known as conjugated hyperbilirubinemia, constitutional hepatic dysfunction, or familial nonhemolytic jaundice) will be permitted.
6. Bariatric, gastric bypass, and other gastrointestinal procedures or surgeries (including all types of gastric banding, restriction, and/or LapBand®) with the objective of promoting weight loss within the past two years at Screen Visit.
7. Medical history of cancer (except for resected non-invasive basal or squamous cell carcinoma) and/or treatment for cancer within the last 5 years.
8. Blood dyscrasias or any disorders causing hemolysis or unstable red blood cells (e.g., malaria, babesiosis, haemolytic anaemia).
9. Treatment with GLP-1 analogues within 3 months prior to Informed Consent.

